6 STUDY SCHEDULE AND ASSESSMENTS

6.1 Efficacy Parameters

6.1.1 Itch Numeric Rating Scale

The Itch NRS is a validated, self-reported instrument for measurement of itch intensity. It uses a 24-hour recall period and asks subjects to rate the intensity of their itch on an 11-point

scale ranging from 0 (no itch) to 10 (worst itch imaginable). Higher scores indicate greater itch intensity. In this study, both worst itch intensity (WI-NRS) and average itch intensity (AI-NRS) during a 24-hour recall period will be captured. Subjects will record their Itch NRS scores once daily via eDiary throughout the screening, treatment, and follow-up periods, as outlined in [Appendix A](#).

6.1.2 *Static Patient Global Assessment of Itch Severity*

The sPGA is designed to assess overall itch severity. Each subject is asked to rate the severity of his/her itchiness in the past 7 days on a 5-point scale as none, mild, moderate, severe, and very severe. Higher scores indicate greater itch severity. The sPGA scores will be captured via eDiary as outlined in [Appendix A](#).

6.1.3 *Patient Global Impression of Change in Itch Severity*

The PGIC in Itch Severity is a single item used to assess the change in overall itch severity since the baseline visit. Each subject will rate the change in his/her itch severity on a 7-point scale from (very much better) to (very much worse). PGIC scores will be captured via eDiary as outlined in [Appendix A](#).

6.1.4 *ItchyQoL*

ItchyQoL is a validated, pruritus-specific instrument that measures the degree to which pruritus affects quality of life (QoL).²⁹ This impact is quantified into 3 subscores (symptom, function, emotion) and an overall score. A higher score corresponds to a more adverse impact on QoL. Subjects will complete ItchyQoL as outlined in [Appendix A](#).

6.1.5 *5-D Pruritus Scale*

The 5-D Pruritus Scale is a validated, multi-dimensional measure of itching that assesses the five domains of degree, duration, direction, disability and distribution. Subjects rate their symptoms over the preceding 2-week period on a 1 to 5 scale, with 5 being the most affected. Subjects will complete the 5-D Pruritus Scale during study visits as outlined in [Appendix A](#).

6.1.6 *Actigraphy*

High-resolution actigraphy is an objective method for quantifying nocturnal scratching events and sleep-related parameters using high resolution actigraphy devices on each wrist. The device weighs 16g (0.56oz) without the strap, and is made of medical device grade housing material. The device is water resistant up to 10 meters, dust-tight, and drop-resistant to 0.5m. It is functional for operation between 41 and 104 degrees Fahrenheit (5 and 40 degrees Celsius).

The assessment requires each subject to wear the actigraphy devices, which are the size of a medium size wrist watch, on each wrist during sleep, with the option to wear them during waking hours as well. The devices will be programmed and activated prior to being provided to subjects. Once received, the subjects can simply put the devices on their wrists and they will record automatically. The devices are returned to the study site where the data are

downloaded and sent for analysis. Subjects will be permitted to not wear the devices up to three sleep sessions over any seven-day period throughout the study, to allow for cases of temporary irritation or discomfort.

The 3-D acceleration data (m/sec²) from the actigraphy device is analyzed with a neural network that was developed to discriminate scratching from other nighttime events. The algorithm was developed and tested in a study of 24 subjects (6 healthy, 18 with atopic dermatitis) who were video recorded for one night in a sleep lab while wearing actigraphy devices on each wrist. The video recordings were scored to quantify the time and duration of each scratching event. A strong correlation was shown ($r = 0.98$) between the number of scratching events per hour measured with the actigraphy analysis versus the video scoring. In contrast, subjective questionnaires completed by the subjects the following morning had a poor correlation with the true number of scratching events. For example, the best correlation was 0.6 with a VAS. The full description of the algorithm and the study has been submitted to *IEEE Journal of Biomedical and Health Informatics*.³⁰

Actigraphy measurements will be assessed as outlined in [Appendix A](#).

6.1.7 *Investigators' Global Assessment of Atopic Dermatitis Severity*

The IGA-AD is an instrument used to assess the overall severity of atopic dermatitis at a given time point, as determined by the investigator. It consists of a 6-point scale ranging from 0 (clear) to 5 (very severe). The IGA-AD uses clinical characteristics of erythema, infiltration, papulation, oozing and crusting as guidelines for the overall severity assessment.³¹ IGA-AD scores will be assessed as outlined in [Appendix A](#).

6.2 *Safety Parameters*

Safety assessments will consist of monitoring and recording protocol-defined AEs and SAEs; vital signs; physical examinations; clinical laboratory assessments; ECGs; pharmacokinetics (PK) measurements; and other protocol-specified tests that are deemed critical to the safety evaluation of the study drug.

6.2.1 *Vital Signs*

Vital signs will include measurements of heart rate, sitting blood pressure, respiration rate, and temperature. Vital signs will be assessed as outlined in [Appendix A](#) and at unscheduled study visits when clinically indicated. The subjects' height and weight will be measured as outlined in [Appendix A](#).

6.2.2 *Physical Examination*

Physical examinations will be performed as outlined in [Appendix A](#) and at unscheduled study visits when clinically indicated. A complete physical examination will be performed at the initial Screening visit, while subsequent examinations may be abbreviated and targeted to changes in disease activity and/or subjects' symptoms.

6.2.3 Clinical Laboratory Assessments

Samples for hematology, chemistry, urinalysis, and serum pregnancy testing (when necessary) will be collected as outlined in [Appendix A](#) and at unscheduled study visits when clinically indicated, and analyzed at a central laboratory unless otherwise specified. Detailed instructions regarding sample collection, preparation, and shipment can be found in the laboratory manual. Laboratory assessments will include the following:

- Hematology: hematocrit, hemoglobin, red blood cell count, red blood cell indices, platelets, white blood cell count, white blood cell differential (neutrophils, lymphocytes, monocytes, basophils, eosinophils)
- Chemistry: sodium, potassium, chloride, bicarbonate, glucose, blood urea nitrogen (BUN), creatinine, calcium, phosphorus, magnesium, albumin, ALT, AST, alkaline phosphatase, total bilirubin, LDH, uric acid, total protein, lipid panel
- Pregnancy testing: all females of childbearing potential will have a local urine pregnancy test performed. Positive or equivocal urine pregnancy test results will be confirmed by a serum pregnancy test analyzed at a central laboratory
- Urinalysis: color, clarity, pH, specific gravity, bilirubin, glucose, ketones, leukocytes, nitrite, blood, protein, urobilinogen, microscopic analysis
- Endocrine and cardiac: TSH, free T4, cortisol, corticotropin, troponin
- Reproductive endocrine (for all female subjects): serum FSH, LH, estradiol, progesterone

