6.5.1 Informed Consent/Assent

Informed consent will occur prior to any protocol-mandated procedures, including the stopping of any excluded therapies. This may occur prior to the initial Screening visit.

6.5.2 *Screening Visit/Period*

An initial Screening visit should be scheduled to occur 14 days (-2 days, +3 days) prior to the Baseline visit. The following screening procedures are to be performed at the initial Screening visit:

- Inclusion/exclusion criteria review
- Medical history
- Complete physical examination
- Vital signs (including height and weight)
- IGA-AD
- 5-D Pruritus Scale
- ECG
- Schedule the baseline visit
- Provide actigraphy device with instructions
- Provide eDiary with instructions

During the screening period (after consent/assent and prior to the baseline visit), the following screening procedure is to be performed:

- Laboratory
 - Reproductive endocrine labs for females
 - Urine pregnancy test for females of childbearing potential (with positive or equivocal results confirmed by a serum pregnancy test)
 - Endocrine and cardiac
 - Hematology
 - Chemistry
 - Urinalysis

6.5.3 *Baseline Visit*

The Baseline visit occurs 14 days (-2 days, +3 days) after the Screening visit. At the Baseline visit, the following procedures and assessments are to be performed:

- Inclusion/exclusion criteria review
- Vital signs

- IGA-AD
- 5-D Pruritus Scale
- Concomitant medications
- AEs
- Randomization if eligible
- Dispense study drug
- Schedule future visits

Randomized subjects will begin treatment with study drug in the evening of the Baseline visit (Study Day 1).

6.5.4 *Week 1 Visit*

The Week 1 visit is a telephone visit that occurs 7 days (± 3 days) after the Baseline visit (Study Day 5-11). At the Week 1 visit, the following procedures and assessments are to be performed:

- Concomitant medications
- AEs

6.5.5 *Week 2 Visit*

The Week 2 visit occurs 14 days (± 2 days) after the Baseline visit (Study Day 13-17). At the Week 2 visit, the following procedures and assessments are to be performed:

- Vital signs (including weight)
- IGA-AD
- 5-D Pruritus Scale
- Targeted physical examination
- ECG
- Laboratory
 - Urine pregnancy test for females of childbearing potential (with positive or equivocal results confirmed by a serum pregnancy test)
 - Hematology

- Chemistry
- Urinalysis
- PK blood sample collection
- Concomitant medications
- AEs
- Collect returned study drug
- Dispense study drug

6.5.6 *Week 4 Visit*

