7.1.5 Pregnancies and Contraception Requirements for Males and Females

For the purposes of this study, a female of childbearing potential is defined as any female who has experienced menarche and is pre-menopausal; a postmenopausal state is defined as no menses for 12 months without an alternative medical cause in a previously menstruating female. A fertile male is defined as any male who is post-pubertal and not castrated (e.g. history of bilateral orchiectomy) or sterilized (i.e. history or vasectomy).

For the purposes of this study, acceptable contraception is defined below based on *Nonclinical Safety Studies for the Conduct of Human Clinical Trials and Marketing Authorization for Pharmaceuticals: ICH M3(R2)* dated January 2010, and other available guidelines^{32,33,34}.

1. For female subjects: All female subjects of childbearing potential must use highly effective contraception, which includes the use of one or more of the following acceptable methods:
 - a. Surgical sterilization (e.g., bilateral tubal occlusion or ligation, hysterectomy, bilateral salpingectomy, bilateral oophorectomy)
 - b. Total (as opposed to periodic or cyclic) abstinence

- c. Hormonal contraception associated with consistent inhibition of ovulation; these may include (but are not necessarily limited to) oral, intravaginal, implantable, injectable, or transdermal delivery methods.
 - i. Progesterone only oral contraceptives are excluded as a highly effective method, as they do not consistently inhibit ovulation.
 - d. Intrauterine device/system
 - e. Exclusive monogamous heterosexual intercourse with a sterilized (i.e., vasectomized) or otherwise non-fertile (e.g., castrated) male partner
2. For male subjects: All fertile male subjects, with sexual partners who are females of childbearing potential, must use condoms with or without spermicide.
 3. All subjects who are fertile males or females of childbearing potential must also refrain from sperm/egg donation starting from first dose of study drug and until 4 weeks after last dose of study drug.

Any pregnancy occurring in a female subject or the female partner of a male subject, from the first study drug administration through the 4-week follow-up visit must be reported within 24 hours of the investigator's awareness of the pregnancy. See MTI-103 SAE and Pregnancy Form Completion Instructions for complete instructions.

The investigator will follow the pregnancy to delivery or other pregnancy outcome.

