APPENDIX A SCHEDULE OF ACTIVITIES AND ASSESSMENTS

Table 2 Schedule of Visit Activities

Examination	Consent	Screening	Baseline	Week 1	Week 2	Week 4	Week 6	ETD*	F/U**	Comments & Clarifications
Study Days (D)			D 1	D 8	D 15	D 29	D 43	*	**	
Visit Window in Days (d)			-2d, +3 d	±3 d	±2 d	±3 d	±3 d	*	±3 d	
Informed consent/assent	X									Informed consent will occur prior to any protocol-mandated procedures, including the stopping of any excluded therapies. This may occur prior to the initial Screening visit.
Medical history		X								
I/E criteria		X	X							
Randomization			X							
Physical exam		X			X		X	X	X	Screening physical exam is complete; other exams are targeted
Vital signs		X	X		X	X	X	X	X	Height will be assessed at screening; Weight will be assessed at screening, baseline, Week 2, Week 6, ETD, and F/U
ECG		X			X				X	
Labs		X			X		X	X	X	Screening labs, including urine pregnancy test, may be collected during the screening period (after Screening visit but prior to the Baseline visit); Endocrine and cardiac, and reproductive endocrine labs will be collected at screening, Week 6, ETD, and F/U
PK					X	X	X	X		
IGA-AD		X	X		X	X	X	X	X	
5-D Pruritus Scale		X	X		X	X	X	X	X	
Dispense study drug			X		X	X				
Collect study drug					X	X	X	X		
Concomitant medications			X	X	X	X	X	X	X	
AEs			X	X	X	X	X	X	X	After informed consent/assent, but prior to study drug administration, only SAEs caused by a protocol-mandated intervention will be collected

* Early Treatment Discontinuation (ETD) visit occurs within 7 days of last dose for subjects who discontinue study drug treatment prior to the Week 6 visit

**The Follow-up (F/U) visit occurs 28 days (± 3 days) after the Week 6 visit (Study Day 68-74) or the ETD visit (for subjects who discontinue study drug early). Subjects who discontinue study drug prior to Study Day 15 should have a follow-up visit 6 weeks (± 3 days) after randomization (Study Day 40-46) so that all randomized subjects will have a Week 6 evaluation.

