3.5.2 Clinical Laboratory Evaluations

Summary statistics for actual values and for changes from baseline will be tabulated for clinical laboratory results by analysis window. Shifts from baseline clinical laboratory values based upon the normal range will be tabulated. These tables will utilize the normal ranges provided for the individual sample.

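### FSH, LH, estradiol and progesterone are drawn in all females with no menstrual date specified and tabulated pooled over reproductive status, so these safety tables are weakly informative for cycling women

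*Protocol*

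**What the plan says.** Protocol 6.2.3 lists the panel as "Reproductive endocrine (for all female subjects): serum FSH, LH, estradiol, progesterone", with no condition on cycle, contraception or menopause. Protocol Appendix A, Table 2 sets the times: "Endocrine and cardiac, and reproductive endocrine labs will be collected at screening, Week 6, ETD, and F/U". The same table leaves the day of the pre-treatment draw open: "Screening labs, including urine pregnancy test, may be collected during the screening period (after Screening visit but prior to the Baseline visit").

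The visit lists in Protocol 6.5 include no menstrual date or cycle day. Menses are mentioned only in Protocol 7.1.5, where childbearing potential and the post-menopausal state are defined. That section accepts "Hormonal contraception associated with consistent inhibition of ovulation" as one contraceptive method beside others, such as an intrauterine device, abstinence or a sterilized partner, that need not suppress ovulation. Protocol 5.7.1 lets oral contraceptives and hormone replacement continue, and entry is from age 13.

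SAP 3.5.2 has one rule for all laboratory tests: "Summary statistics for actual values and for changes from baseline will be tabulated for clinical laboratory results by analysis window", and "Shifts from baseline clinical laboratory values based upon the normal range will be tabulated". The ranges used are those supplied with each sample. SAP 3.1 makes the summaries by treatment group. The subgroups in SAP 2.8 apply to WI-NRS only.

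**The concern.** Change in laboratory parameters is a named safety endpoint (Protocol 3.3.4, SAP 2.3), and this panel is drawn repeatedly in every female subject, adolescents included. Its evident use is to show whether the drug affects the female endocrine axis.

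The tables combine women whose hormones move with the cycle, women whose ovulation is suppressed, post-menopausal women and possibly premenarchal girls. In cycling women, a change from baseline may only mean that the two samples fell in different phases. An effect confined to cycling women is averaged with women in whom it could not appear. An unremarkable pooled table could then be taken as reassurance that it does not give.

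**Working it through.** The plan states no precision for these hormones. Its only sizing figure is for WI-NRS (150 per group, 90% power; a t-test calculation gives 91%), which is not in dispute.

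**Interval between draws (from the documents).** Protocol 6.5.2: "An initial Screening visit should be scheduled to occur 14 days (-2 days, +3 days) prior to the Baseline visit", so the Screening visit is 12 to 17 days before Baseline. Protocol 6.5.7 puts Week 6 at 42 ± 3 days, so 39 to 45 days after Baseline.
- Nominal: 14 + 42 = 56 days, which is two 28-day cycles.
- Draw at the Screening visit: 12 + 39 = 51 to 17 + 45 = 62 days.
- Draw on any day before Baseline: 1 + 39 = 40 to 62 days.

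**Phase change between draws (assumed: regular cycles, 14-day luteal phase, random starting phase, each permitted day equally likely, no drug effect).** For a 28-day cycle, let d be the distance in days from the interval to the nearest multiple of 28. The probability that the two draws fall in different phases is 2d/28 = d/14.
- Draw 12 to 17 days before Baseline: 6 × 7 = 42 day pairs, sum of d = 91, mean 2.17, so 2.17/14 = 0.15.
- Draw 1 to 17 days before Baseline: 17 × 7 = 119 day pairs, sum of d = 699, mean 5.87, so 5.87/14 = 0.42.

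For cycle lengths L spread evenly over 25 to 32 days, the probability is 2·min(d, 14, L − 14)/L, with d measured to the nearest multiple of L. The averages are 0.28 and 0.48.

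**Noise from phase alone (assumed progesterone: 0.5 ng/mL follicular, 10 ng/mL luteal).** The change is +9.5, −9.5 or 0 with mean zero, so SD = 9.5 × √p, where p is the probability of a phase change. With 40 cycling women per arm (assumed), the 95% half-width of the arm difference is 1.96 × SD × √(2/40).

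| Screening draw, days before Baseline | p, 28-day cycles | p, 25–32 days | SD of change (ng/mL) | Half-width (ng/mL) |
|---|---|---|---|---|
| 12–17 | 0.15 | 0.28 | 3.7 to 5.0 | 1.6 to 2.2 |
| 7–17 | 0.25 | 0.35 | 4.7 to 5.6 | 2.1 to 2.5 |
| 1–17 | 0.42 | 0.48 | 6.2 to 6.6 | 2.7 to 2.9 |

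Across the same timings, an assumed luteal level of 5 ng/mL gives half-widths of about 0.8 to 1.4, and 15 ng/mL gives about 2.5 to 4.4.

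**Sensitivity to regular cycles.** A separate simulation used cycles averaging 28.5 days (SD 2.5 between women, 1 to 4 days within) and a 13-day luteal phase. Phase change was 32% to 41% for draws at the Screening visit and 48% to 50% for draws on any day. Chance alone gives about 50%.

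**Dilution.** If a fraction f of the females in an arm is cycling and only they respond, an effect δ appears in the pooled table as fδ. With f assumed at 30% to 50%, the displayed mean change is 0.3δ to 0.5δ. If the other women added no variance, the pooled SD would shrink by √f and the signal-to-noise ratio would be that of the cycling women alone. Dilution therefore costs power only through the other women's own variability, but it always shrinks the figure shown.

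**The case against.** **What stands.**
- The laboratory manual and the eCRF are not among the documents, and 7.1.5 obliges sites to take some menstrual history. It can be said only that the protocol and SAP specify no menstrual date, not that none is collected.
- Menopausal status and stable contraception hardly change within a woman over about eight weeks, so they largely cancel in a change from baseline. Only cycle phase adds noise to it. Mixed status matters more for the tables of actual values.
- Shift tables use the range supplied with each sample, which may reflect age or status. It can reflect phase only if the laboratory is told the phase.
- Screening chemistry decides exclusion criterion 14 and goes to a central laboratory. A draw on the last day before Baseline is permitted but unlikely, so the lower half of the range may be nearer practice.
- The tables are descriptive. Results are also listed by subject (SAP 2.3.9), and clinically significant abnormalities become adverse events (Protocol 7.1.3).

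**What does not defeat the point.** Even if menstrual dates are captured elsewhere, the SAP makes no use of them and plans no split by status.

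**Stronger readings to avoid.** A reader might infer that cycle phase, contraception and menopause swamp any drug effect, or that most tabulated shifts are phase changes. The documents give no hormone variances and no effect size of interest, so neither follows. A large effect, or one in post-menopausal women, could still show.

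**Conclusion.** The point holds as one of limited information, not bias. The plan draws four cycle-dependent hormones in all females, specifies no menstrual date, and pools the results over reproductive status within arm. For cycling women the resulting tables say little.

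The share changing phase between draws is about 15% to 28% or 42% to 48%, depending on when in screening the sample is taken, and higher in the first case if cycles vary within a woman. The half-width of about 1.6 to 2.9 ng/mL for progesterone rests on assumed hormone levels, assumed cycle regularity and an assumed 40 cycling women per arm; none of these is in the documents. The primary analysis, the sample size and the other safety tables are untouched. This is a worthwhile refinement rather than a necessary correction.

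**What to change.** 1. In SAP 3.5.2, present the four hormones by arm separately for premenarchal females, post-menopausal women, pre-menopausal women on hormonal contraception, and other menstruating women. Use the 7.1.5 definitions and the recorded medications. State in advance where women without menses for surgical reasons are placed. This is an SAP edit and can be made even if data collection cannot change.
2. If the eCRF or laboratory requisition does not already capture it, record the first day of the last menses at each existing reproductive-endocrine draw.
3. For menstruating women, summarize values descriptively by phase at each draw, and show normal-range shifts only where the supplied range is phase-specific.
4. Keep the comparison of all menstruating women as the main one. Any change restricted to same-phase draws should be supportive only: phase after randomization could be affected by the drug, so conditioning on it could hide or distort the effect sought.

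Cost: one additional table layout, one date field and smaller groups in each table. No new samples or visits are needed.

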6.2.4 Electrocardiogram

A standard 12-lead ECG will be performed as outlined in [Appendix A](#) and at unscheduled study visits when clinically indicated.

[figure not shown]
6.3 Pharmacokinetics Measurements

Sparse PK sampling will collect one PK sample at each of the Week 2, Week 4, and Week 6 visits as well as the ETD visit as outlined in [Appendix A](#). The date and time of dosing prior to PK sample collection and date and time of PK sample collection will be recorded in the eCRF. Detailed instructions regarding PK sample collection, preparation, and shipment can be found in the laboratory manual.

